5.1 Mapatumumab and Placebo

5.1.1 Formulation

Mapatumumab will be supplied as a lyophilized formulation in sterile, single-use 10 mL vials containing 100 mg mapatumumab. Upon reconstitution with 5.0 mL of sterile water for injection, each vial will contain 20 mg/mL mapatumumab in 0.13 mg/mL citric acid, 2.8 mg/mL sodium citrate, 19 mg/mL glycine, 5 mg/mL sucrose, 0.2 mg/mL polysorbate 80, pH 6.5.

Two hundred-fifty mL normal saline solution for intravenous infusion will be administered as placebo for mapatumumab.

5.1.2 Packaging, Labeling, Preparation, and Storage

The Pharmacy Manual will provide instructions for preparation and storage of study agent. The product will be securely stored at 2-8°C.

The study agent label will contain, at a minimum, the following information:

- Product name
- Concentration

- Lot number
- Storage instructions
- Investigational drug statement
- Manufacturer's name and address

Study agent inventory/accountability forms will be examined and reconciled by the unblinded study monitor or designee. At the end of the study, all used and unused investigational study agent will be accounted for on a study agent accountability form provided to the investigator by the Sponsor or designee. Please refer to the HGS1012-C1103 Pharmacy Manual for more details regarding storage, handling and drug accountability.

5.1.3 Mapatumumab/Placebo Dose, Route of Administration and Schedule

The dose of mapatumumab is 30 mg/kg. Mapatumumab dose calculations will be based upon the subject's weight measured on Day 1 or within 3 days before Day 1 of each cycle. The planned duration of each treatment cycle will be 21 days. Mapatumumab/placebo will be administered on Day 1 of each cycle.

After reconstitution with sterile water for injection, the calculated mapatumumab dose to be administered to the subject will be further diluted in normal saline to a total volume of 250 mL for intravenous infusion. After adding the reconstituted product, the bag will be gently inverted to mix the solution. Following reconstitution and/or dilution in normal saline, mapatumumab will be stored at 2-8°C. The product will be administered to the subject within 8 hours of reconstitution. Refer to the HGS1012-C1103 Pharmacy Manual for instructions on admixing and administering study agent.

Two hundred-fifty mL normal saline solution for intravenous infusion will be administered as placebo for mapatumumab.

Mapatumumab/placebo will be infused at a constant rate over 1 hour.

Infusion and hypersensitivity reactions may occur. A suggested pre-medication regimen for mapatumumab/placebo consists of diphenhydramine and acetaminophen administered within 1 hour prior to the start of the mapatumumab/placebo dose. Use of a pre-medication regimen and alternatives to this regimen are at the investigator's discretion.

Subjects will be monitored closely during and after infusion for any sign of acute adverse reaction. If an allergic reaction occurs, see Section [5.1.5](#) and [Appendix 8](#) for suggested medical management.

5.1.4 Mapatumumab/Placebo Dose Toxicity/Delay

Mapatumumab/placebo will be discontinued for Grade 4 transaminase elevations of any duration if they are considered related to mapatumumab.

AM01
21Dec10

Mapatumumab/placebo may be delayed up to 2 weeks for toxicities considered related to mapatumumab as described below or if the investigator believes that a delay in dosing is warranted in the interest of subject safety.

The National Cancer Institute Common Terminology Criteria for Adverse Events (NCI-CTCAE, Version 4.0) will be used to grade AEs.

- Grade 4 neutropenia for > 7 consecutive days or febrile neutropenia.
- Grade 4 thrombocytopenia.
- Grade 3 or greater non-hematologic AEs except transient transaminase, amylase and lipase abnormalities for which the following criteria will apply:
 - Grade 3 or Grade 4 elevations in transaminases that do not resolve to baseline or Grade 1 before the next cycle.
 - Grade 3 elevations in lipase or amylase associated with clinical/imaging findings of pancreatitis, or resulting in chronic damage to the pancreas.
 - Any Grade 4 elevations in lipase or amylase for > 4 consecutive days.

If mapatumumab/placebo is delayed for toxicity and the toxicity does not resolve (\leq Grade 1) or return to baseline within 2 weeks after the delayed dose was originally scheduled (based on a 21-day treatment cycle), the subject will be withdrawn from further treatment with mapatumumab/placebo. If mapatumumab/placebo is delayed because the investigator believes a delay is warranted in the interest of subject safety and dosing of mapatumumab/placebo is not resumed within 2 weeks after the delayed dose was originally scheduled (based on a 21-day treatment cycle), the subject will be withdrawn from future treatment with mapatumumab/placebo. Sorafenib dosing will continue while mapatumumab/placebo dosing is held. The subject will continue receiving sorafenib until radiologic progressive disease or an unacceptable toxicity occurs, at the discretion of the Investigator.

Doses of mapatumumab may not be altered.

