The Human Genome Sciences Review Committee (HGSRC) is comprised of the Department Heads of Biostatistics, Regulatory Affairs and Drug Development. The HGSRC will review safety data after: (1) 10 subjects have completed 1 cycle; and (2) 30 subjects have completed 1 cycle. HGSRC reviews of safety data will be conducted approximately every 4 months thereafter, until 90% of subjects have reached radiologic progression. The HGSRC may conduct additional reviews at their own request and/or at the request of the Medical Monitor. The HGSRC may request the unblinding of treatment assignment for a subject and/or treatment groups. If treatment assignments are unblinded, the rationale for the unblinding will be documented.

Immunogenicity:

Blood samples for serum antibodies to mapatumumab will be obtained as outlined in Table 6-1.

Dose Modification/Delay:

Dose modifications will not be allowed for mapatumumab/placebo. Dose modifications of sorafenib for toxicity will be made according to the guidelines provided in the treatment section (Section [5.2.3](#)) of the protocol.

Details regarding pre-treatment and management of hypersensitivity reactions related to mapatumumab are provided in Section [5.1.5](#) and [Appendix 8](#).

Pharmacokinetics:

Multiple blood specimens will be obtained from subjects for serum mapatumumab concentration determinations as outlined in [Table 6-1](#).

Pharmacodynamics:

Subjects will be given the option to participate in a biomarker research sub-study. Consenting subjects will be asked to provide a historically obtained biopsy sample, if available, and several blood samples. In addition, samples will be requested from subjects who undergo a biopsy during the treatment period.

To examine biomarkers present peripherally, blood will be drawn during Cycles 1 and 2, from which DNA and serum proteins will be isolated. The biomarker sub-study is detailed in [Appendix 6](#).

Exploratory Assessments:

Blood samples will be collected for quantification of B and T lymphocyte subsets on Day 1 (prior to dosing) and Day 15 of Cycles 1 and 2.

Study Endpoints:

The following will be evaluated (these endpoints and the respective analyses are defined in Section [9](#)):

Primary:

- Time to progression (TTP).

Secondary:

- Overall survival.
- Progression-free survival.
- Objective response (complete response [CR] + partial response [PR]).
- Disease control (CR + PR + stable disease [SD]).
- Response duration and time to response in responders.

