3.1 Basic Design Characteristics

This is a Phase 2, multi-center, randomized, double-blind, placebo-controlled study to evaluate the efficacy and safety of mapatumumab in combination with sorafenib in subjects with advanced hepatocellular carcinoma.

In addition to receiving sorafenib, subjects will be randomly assigned to 1 of 2 treatment groups in a 1:1 ratio: 30 mg/kg mapatumumab or placebo.

Mapatumumab will be supplied in open label vials and 3rd party unblinding will be employed. The study agent will be reconstituted by the unblinded site pharmacist or unblinded designee. The unblinded site pharmacist or unblinded designee will also be the person responsible for receiving and dispensing study agent, but independent of all other study activities. All other study site personnel, the subject, and the Sponsor will remain blinded to the study agent received. Separate monitors will be responsible for the clinical (blinded monitor) and study agent (unblinded monitor) aspects of the study.

Number of Subjects:

Approximately 100 subjects with advanced HCC will be randomized/enrolled.

Treatment Groups:

Subjects will receive treatment every 21 days (ie, a cycle) as outlined below:

Arm A: Sorafenib 400 mg orally twice daily continuously in each cycle + placebo intravenously on Day 1 of each cycle

Arm B: Sorafenib 400 mg orally twice daily continuously in each cycle + mapatumumab (30 mg/kg) intravenously on Day 1 of each cycle

Randomization

Randomization will be stratified according to BCLC advanced stage C vs BCLC intermediate stage B and ECOG performance status (0 vs 1, 2).

Estimated Study Duration:

The study is estimated to occur over approximately 24 months. Subjects will continue to receive sorafenib with or without mapatumumab/placebo until radiologic disease progression or unacceptable toxicity. Estimated median length of subject treatment is 6-8 months. Subjects who completed more than 24 months of study treatment with mapatumumab and/or sorafenib and who in the opinion of the investigator obtain clinical benefit from treatment, will be allowed to continue treatment with unblinded mapatumumab and/or sorafenib in the clinical trial. This extension of treatment will continue until the subject's disease progresses or they withdraw from study. In addition extension of treatment with mapatumumab will not extend beyond the expiry date of the drug batch (March 2016).

AM03
15Jul15

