5.2.3 Alteration of Sorafenib Dose/Schedule Due to Toxicity

Sorafenib may be reduced or delayed for toxicities considered related to sorafenib as described below, or if the investigator believes that a reduction in dose is warranted in the interest of subject safety. When a dose reduction is necessary, sorafenib dose may be reduced to 400 mg once daily. If an additional dose reduction is required, sorafenib may be reduced to a single 400 mg dose every other day (see [Table 5-1](#)). A maximum of 2 dose reductions of sorafenib will be allowed per subject. Additional dose reductions not mentioned in [Table 5-1](#) will need to be discussed with the medical monitor.

Table 5-1 Sorafenib dose levels

Dose Levels	Sorafenib
0	400 mg twice daily
-1	400 mg once daily
-2	400 mg once every other day

Skin toxicity and hypertension are associated with sorafenib. Guidelines for the management of these events are provided in [Table 5-2](#) and [Table 5-3](#), respectively.

Skin Toxicity

Hand-foot skin reaction and rash are common in subjects treated with sorafenib. Management may include topical therapies for symptomatic relief, temporary treatment interruption and/or dose modification, or in severe or persistent cases, permanent discontinuation. Skin toxicities will be managed according to [Table 5-2](#).

Table 5-2 Dose modifications of sorafenib for skin toxicity

Skin Toxicity Grade	Occurrence	Suggested Dose Modification
Grade 1: Numbness, dysesthesia, paresthesia, tingling, painless swelling, erythema or discomfort of the hands or feet which does not disrupt the subject's normal activities.	Any occurrence	Continue treatment with sorafenib and consider topical therapy for symptomatic relief.
Grade 2: Painful erythema and swelling of the hands or feet and/or discomfort affecting the subject's normal activities.	1 st occurrence	Continue treatment with sorafenib and consider topical therapy for symptomatic relief. If no improvement within 7 days, see below.
	No improvement within 7 days or 2 nd or 3 rd occurrence	Interrupt sorafenib treatment until toxicity resolves to Grade 0-1. When resuming treatment, decrease sorafenib dose by 1 dose level (400 mg daily or 400 mg every other day).
Grade 3: Moist desquamation, ulceration, blistering or severe pain of the hands or feet, or severe discomfort that causes the subject to be unable to work or perform activities of daily living.	4 th occurrence	Discontinue sorafenib treatment.

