	1 st or 2 nd occurrence	Interrupt sorafenib treatment until toxicity resolves to Grade 0-1. When resuming treatment, decrease sorafenib dose by 1 dose level (400 mg daily or 400 mg every other day).
	3 rd occurrence	Discontinue sorafenib treatment.

Hypertension

Hypertension is a known and potentially serious adverse event associated with sorafenib treatment. Subjects will have their blood pressure monitored and recorded. If the subject's blood pressure is elevated at any time ($> 150/100$ mmHg), even outside clinic visits, they will contact their study investigator. Guidelines for the management of hypertension are provided in [Table 5-3](#).

Table 5-3 Dose modifications of sorafenib for hypertension

Grade (CTCAE v3.0)	Antihypertensive Therapy	Blood Pressure Monitoring	Sorafenib Dose
Grade 1	None	Routine	No change
Grade 2 (asymptomatic)	Initiate monotherapy (suggest dihydropyridine calcium channel blocker)	Increase frequency and monitor by a health professional every 2 days until stabilized.	No change
Grade 2 (symptomatic/ persistent) OR diastolic BP > 110 mm Hg	Add agent(s): calcium channel blocker (if not already used), K ⁺ channel opener (angiotensin blockers), beta-blocker, thiazide diuretic	Increase frequency and monitor by health professional every 2 days until stabilized; continue monitoring every 2 days to stabilization after dosing restarted.	Hold* sorafenib until symptoms resolve and diastolic BP < 100 mm/Hg
Grade 3			Resume treatment at 1 dose level lower**
Grade 4	Discontinue sorafenib	Discontinue sorafenib	Discontinue sorafenib

*Subjects requiring a delay of > 21 days will discontinue sorafenib, unless in the study investigator's opinion, the subject may benefit from continued treatment.

AM01
21Dec10

**Subjects requiring > 2 dose reductions will discontinue sorafenib.

BP = Blood pressure.

Refer to NCI-CTCAE v4.0 for grade definitions.

(concluded)

Guidelines for the management of other non-hematologic and hematologic sorafenib-associated toxicities are provided in [Table 5-4](#). Those toxicities that are at least possibly related to an interaction with mapatumumab/placebo will have the mapatumumab toxicity guidelines in Section [5.1.4](#) applied.

Table 5-4 Dose modifications of sorafenib for sorafenib-associated toxicity

Toxicity	Grade 1	Grade 2	Grade 3*	Grade 4*

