Non-hematologic	Continue at the same dose level	Continue at the same dose level	Withhold dose until toxicity is Grade ≤ 1, then resume treatment at the same dose level. If subject experiences a 2 nd Grade 3 toxicity, withhold dose until toxicity is Grade ≤ 1, then reduce dose to 400 mg orally daily and resume treatment.	Withhold dose until toxicity is Grade ≤ 1, then reduce dose to 400 mg daily and resume treatment, or discontinue at the discretion of the principal investigator after discussion with study sponsor.
Hematologic	Continue at the same dose level	Continue at the same dose level	Withhold dose until toxicity is Grade ≤ 2, then resume treatment at the same dose level. If subject experiences a 2 nd Grade 3 toxicity, withhold dose until toxicity is Grade ≤ 2, then reduce dose to 400 mg orally daily and resume treatment.	Withhold dose until toxicity is Grade ≤ 2, then reduce dose to 400 mg daily and resume treatment, or discontinue at the discretion of the principal investigator after discussion with study sponsor.

See [Table 5-2](#) and [Table 5-3](#) for dose modifications due to skin toxicity and hypertension respectively.

*Subjects who develop Grade 3 fever/chills, Grade 3 elevation of hepatic transaminases with ALT and AST < 10X upper limit of normal, Grade 3 hyperlipasemia or hyperamylasemia without clinical or other evidence of pancreatitis, Grade 3 leukopenia, or Grade 3/Grade 4 lymphopenia may continue sorafenib treatment without interruption at the discretion of the investigator.

Sorafenib Discontinuation

Temporary or permanent discontinuation of sorafenib will be considered in subjects who develop cardiac ischemia and/or infarction or severe or persistent hypertension despite institution of antihypertensive therapy. If a subject experiences a bleeding event that necessitates medical intervention or a gastrointestinal perforation, sorafenib will be permanently discontinued. Subjects, who undergo a surgical procedure or intervention to decrease portal hypertension, including transjugular intrahepatic portosystemic shunt, will discontinue sorafenib.

If the subject is withdrawn from further treatment with sorafenib, the subject may continue to receive mapatumumab/placebo alone every 21 days until radiologic progression or unacceptable toxicity.

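### When mapatumumab/placebo is held during a toxicity also attributed to sorafenib, Section 5.1.4 read literally says to continue sorafenib while Section 5.2.3 says to withhold it (minor, patient safety)

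*Protocol*

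**What the plan says.** Protocol Section 5.1.4 allows a mapatumumab/placebo dose to be delayed by up to 2 weeks. The reason may be a listed toxicity considered related to mapatumumab, or the investigator's judgement that a delay is in the interest of subject safety. The list includes Grade 4 thrombocytopenia and, with qualifications for transaminases, lipase and amylase, non-hematologic events of Grade 3 or higher. The section then says "Sorafenib dosing will continue while mapatumumab/placebo dosing is held", followed by: "The subject will continue receiving sorafenib until radiologic progressive disease or an unacceptable toxicity occurs, at the discretion of the Investigator".

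Section 5.2.3 covers sorafenib. It opens: "Sorafenib may be reduced or delayed for toxicities considered related to sorafenib as described below". What follows is Tables 5-2 (skin), 5-3 (hypertension) and 5-4 (other sorafenib-associated toxicity). For Grade 4 hematologic toxicity, Table 5-4 says: "Withhold dose until toxicity is Grade ≤ 2, then reduce dose to 400 mg daily and resume treatment, or discontinue at the discretion". For Grade 3 or 4 non-hematologic toxicity it withholds until Grade 1 or less. Its footnote lists events for which sorafenib may go on uninterrupted; thrombocytopenia is not among them.

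Three other places matter:

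- The synopsis, under Dose Modification/Delay, says: "Dose modifications of sorafenib for toxicity will be made according to the guidelines provided in the treatment section", and names Section 5.2.3.
- Section 5.2.3, just before Table 5-4, says: "Those toxicities that are at least possibly related to an interaction with mapatumumab/placebo will have the mapatumumab toxicity guidelines" of Section 5.1.4 applied.
- Section 8.6 provides that an event related to sorafenib is recorded as related to both agents when there is evidence that mapatumumab/placebo contributed to it or made it worse.

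**The concern.** The two agents share toxicities, and the protocol expects some events to be attributed to both. For such an event, a site that looks up the mapatumumab/placebo hold reads that sorafenib goes on. A site that looks up the sorafenib table reads that it is withheld. The one cross-reference between the two rule sets points towards 5.1.4, where the instruction is to continue.

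What is at stake is patient safety. Continuing sorafenib through Grade 4 thrombocytopenia is what Table 5-4 is there to prevent. Section 5.2.2 lists both thrombocytopenia and increased bleeding risk as anticipated with sorafenib, and Section 4.1 admits subjects with platelets as low as 50,000/mm³. The situation is plausible: Section 1.6 reports severe thrombocytopenia, at least possibly related to mapatumumab or its interaction with sorafenib, in 1 of 16 Phase 1b subjects (CTCAE grade not given).

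**Working it through.** No power or alpha figure is involved, so the check is a comparison of rules followed by a bound on how many subjects the wording can still affect.

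**Rule comparison.** Take Grade 4 thrombocytopenia, except in the last row, and vary the attribution and whether a mapatumumab/placebo dose is being held.

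| Case | Section 5.1.4 on sorafenib | Section 5.2.3 on sorafenib | Conflict? |
|---|---|---|---|
| Mapatumumab only; dose held | Continues | Table 5-4 not triggered | No |
| Sorafenib only; no dose held | Sentence not triggered | Withhold to Grade ≤ 2 | No |
| Sorafenib only; investigator also delays mapatumumab/placebo for safety | Continues | Withhold to Grade ≤ 2 | Yes |
| Both agents, or interaction; dose held | Continues | Withhold to Grade ≤ 2 | Yes |
| Both agents; mid-cycle, no dose due | Sentence not yet triggered | Withhold to Grade ≤ 2 | Not until a dose is due and held |
| Event in Table 5-4 footnote (e.g. Grade 4 lymphopenia) | Continues if a dose is held | May continue | No |

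The mid-cycle row follows from Section 5.1.3: "Mapatumumab/placebo will be administered on Day 1 of each cycle". Between those days there is normally no mapatumumab/placebo dose to hold. The hold is also optional under 5.1.4, so the conflict needs an investigator who actually uses it.

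**Does the text settle the two conflicting rows?**

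- The sentence after the quoted one in 5.1.4 stops sorafenib for unacceptable toxicity at the investigator's discretion. It is worded as an end point for treatment. It sets no temporary hold, recovery grade or restart dose.
- The cross-reference in 5.2.3 applies the 5.1.4 guidelines to interaction toxicities. It says neither that they add to Table 5-4 nor that they replace it.
- No sentence says which of the two instructions prevails.

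**Remaining scope under Amendment 3.**

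- Enrollment (Section 3.1): "Approximately 100 subjects with advanced HCC will be randomized/enrolled". Appendix 9, item 4, says at least 90% had met the survival endpoint. Subjects still alive: at most (1 − 0.90) × 100 = about 10, both arms together.
- Section 6.4 limits Extended Access to subjects with more than 24 months of study treatment and ends mapatumumab by the batch expiry in March 2016. From 15 July 2015 that is 230 days to 1 March 2016 and 260 days to 31 March 2016, roughly 7.5 to 8.5 months.
- The number of these subjects on mapatumumab is not stated. A subject on sorafenib alone has no mapatumumab dose to hold, so the number at risk may be well below 10.

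**The case against.** The best case against the point is that the protocol is already organized by agent. The synopsis sends sorafenib dose changes to 5.2.3 with no carve-out for shared events, and the section titles make the same split. Read that way, the 5.1.4 sentence means only that a mapatumumab/placebo hold does not by itself stop sorafenib. The cross-reference can also be read as additive: it picks out toxicities that Table 5-4 already covers, and 5.1.4 contains no sorafenib schedule that could take the table's place. This is the natural reading and probably what most sites would do. It lowers the severity. It does not remove the conflict, because it has to be inferred and the literal sentence says otherwise.

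Three stronger readings are tempting, and the documents do not support them.

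- A reader might infer that Section 5.1.4 makes sorafenib continue without exception. That fits the single sentence but not the section, because the next sentence allows sorafenib to stop for unacceptable toxicity at the investigator's discretion.
- A reader might infer that every Grade 4 thrombocytopenia produces contradictory instructions. Each rule set has its own attribution trigger, so an event attributed to one agent alone, with no investigator safety delay, has one clear instruction.
- A reader might infer from the permissive opening of 5.2.3 that it supplies no withhold or restart rule. It does: the opening refers to what is described below it, and the tables that follow give the grades for withholding, the recovery thresholds and the restart doses.

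**Conclusion.** The point holds as a minor patient-safety defect, wrong as written. When mapatumumab/placebo is held for a toxicity also attributed to sorafenib, or is delayed for safety during a sorafenib-related toxicity, the 5.1.4 sentence and the 5.2.3 withhold rules give opposite instructions for sorafenib, and nothing in the protocol ranks them. Grade 4 thrombocytopenia is the clearest example.

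This conclusion rests on the literal text and assumes that the investigator uses the optional hold. How often the situation occurs cannot be determined from the documents; the single Phase 1b case shows plausibility, not a rate. The ceiling of about 10 remaining subjects takes the approximate enrollment as 100 and the 90% figure at its minimum. The same sentence stands in Section 5.1.4 of the original protocol and of Amendments 01 and 02, so the ambiguity was present throughout treatment. Alpha, power, sample size and endpoints are unaffected.

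**What to change.** In Section 5.1.4, extend the sentence "Sorafenib dosing will continue while mapatumumab/placebo dosing is held" with: *unless sorafenib is to be withheld, reduced or discontinued under Section 5.2.3.*

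In Section 5.2.3, after the cross-reference to 5.1.4, add: *For toxicities attributed to both agents, the Section 5.1.4 guidelines apply to mapatumumab/placebo in addition to, not in place of, Tables 5-2 to 5-4 for sorafenib.*

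The cost is one clause and one sentence, with no new procedure, data or analysis. The forward benefit is limited to the few subjects still on treatment and, for mapatumumab, ends by March 2016.
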